6. PROCEDURES

The following procedures/assessments will be conducted according to the schedule indicated in the Table of Events. [Table 5](#) refers to the Table of Events for adult subjects, and [Table 6](#) refers to the Table of Events for adolescent subjects.

6.1. Screening Period

Screening evaluations will be performed for all subjects to determine study eligibility. These evaluations must be completed within 28 days prior to the date of the first dose of IP (study enrollment) unless noted otherwise below. The duration of the Screening Period depends on when active treatment (ie, IP/study drug) is available for the subject at the study center.

6.1.1. Screening Visit

Visits may be completed separately, or combined into a single visit in the following scenarios:

- The Screening Visit 1 from this study and the last study visit from the core GED-0301 study may be combined and completed on the same day.
- The Screening Visit 1 and the Enrollment Visit 2 from this study may be combined and completed on the same day, if the GED-0301-CD-004 study drug is available for the subject at the study center.
- The Screening Visit 1 and the Enrollment Visit 2 from this study and the last study visit from the core GED-0301 study may be combined and completed on the same day, if the GED-0301-CD-004 study drug is available for the subject at the study center.

If 2 visits are combined into a single visit in this study, or if 2 or 3 visits are combined into a single visit from both studies (ie, the core GED-0301 study and this extension GED-0301 study), any visit assessments/procedures which are normally done separately at multiple visits are done only once and not repeated.

If the Screening Visit 1 from this study and the last study visit from the core GED-0301 study are both done separately but are within 14 days of each other, the following Visit 1 clinical and laboratory evaluations do not need to be repeated if they were done at the last study visit from the core GED-0301 study: hematology, chemistry, coagulation, complement activation factors, urinalysis, pregnancy test, ECG, and physical examination.

If all 3 visits (ie, Visit 1 and Visit 2 from this study and the last study visit from the core GED-0301 study) are done separately but all are within a 14-day period, the following clinical, and laboratory evaluations do not need to be repeated if they were done at the last study visit from the core GED-0301 study: hematology, chemistry, coagulation, complement activation factors, urinalysis, pregnancy test, , ECG, physical examination, CDAI,

After informed consent has been obtained, the following assessments will be performed at or following Screening Visit 1 and prior to study enrollment, as specified in the Table of Events

(Table 5 or Table 6), if they were not already completed at the last study visit from the core GED-0301 study:

- Demographics including initials, date of birth, gender, race, and ethnicity (if allowed by local regulations).
- Inclusion/exclusion criteria: Subjects must meet all inclusion criteria (Section 4.2) and must not have any of the conditions specified in the exclusion criteria (Section 4.3) to qualify for participation in the study. The subject's source documents must support his/her qualifications for the study (eg, if a female subject does not require pregnancy testing and birth control because of a hysterectomy, the date of the hysterectomy must be included in the core study's medical history).
- Prior and concomitant procedures evaluation: All procedures occurring at or after Screening Visit 1 should be recorded.
- Prior and concomitant medications evaluation: All ongoing medications from the core GED-0301 study will be electronically carried forward and should not be re-recorded in Prior and Concomitant Medications electronic case report form (eCRF) in this study. However, any new medications (prescription and nonprescription, including vitamins) taken by the subject at and after Screening Visit 1 or at any time during this study must be recorded. Additional instructions can be found in the eCRF Completion Guidelines.
- Adverse event evaluation: Adverse event (AE) assessment begins when the subject signs the informed consent form and is assessed continuously throughout the study, until 28 days following the last dose of IP. All ongoing AEs from the core GED-0301 study will be electronically carried forward and should not be re-recorded in the AE eCRF in this study. However, any new AEs or worsening AEs which occur at and after Screening Visit 1 or at any time during this study must be recorded. Worsening of a subject's CD should be considered as worsening of the disease under study, and should not be captured as an AE unless it meets any of the criteria of a serious adverse event (SAE). Refer to Section 10 for details pertaining to AEs. Additional instructions can be found in the eCRF Completion Guidelines.
- Pregnancy test: A pregnancy test is required for all female subjects of childbearing potential. A local urine pregnancy test will be performed at Screening Visit 1, if not done at the last study visit from the core GED-0301 study. All local urine pregnancy test kits will be provided by the central laboratory. Urine and confirmatory serum pregnancy (ie, serum pregnancy test of the beta-subunit of human chorionic gonadotropin [β -hCG]) tests should be performed if the FCBP has missed a menstrual period, or the contraception method has changed at any time during the study.
- Contraception education (Section 6.5.5)
- Vital signs and weight: Vital signs, including seated blood pressure, temperature, and heart rate will be taken. Weight (to be done in street clothes, no shoes) will also be measured and recorded, if not done at the last study visit of the core GED-0301 study.
- Height, only for the adolescent subjects and should be measured using a stadiometer.

- Complete physical examination (Section 6.5.1), if not done at the last study visit of the core GED-0301 study.
- 12-lead electrocardiogram (ECG) (Section 6.5.2), if not done at the last study visit of the core GED-0301 study.
- Clinical laboratory evaluations will be performed by a central laboratory and will include the following laboratory assessments, if not done at the last study visit of the core GED-0301 study. Details pertaining to the central laboratory assessments and panels are included in Section 6.5.3:
 - Hematology panel
 - Chemistry panel
 - Coagulation panel
 - Complement activation factor panel
 - Urinalysis panel
- Subject daily diary (Section 6.6.1)
 - A new or updated electronic device diary will be provided to the subject at Screening Visit 1 for the collection of the subject daily diary in this study.
 - Subject will receive instructions pertaining to the use of the electronic device and the importance of diary compliance through Week 40 for an adolescent subject.
 - In order to achieve consistent diary recording, the subject is instructed by the site personnel (at each visit if necessary) that he/she is required to enter diary data, each day, through Week 40 for an adolescent subject.
 - Site staff must assess the subject's diary compliance through Week 40 for an adolescent subject.

6.2. Treatment Period

The subject will begin study treatment upon confirmation of all eligibility and availability of IP at the study center. All subsequent visits after the Enrollment Visit (which is the Visit 2/Week 0 Visit) are scheduled based on the date of the Visit 2/Week 0 Visit \pm 3 days, according to the timeframes specified in Table 5 for adult subjects and Table 6 for adolescent subjects. The Follow-up Visit is scheduled 28 days (4 weeks) after the date of the last dose of IP \pm 3 days.

The following Visit 2 clinical and laboratory evaluations do not need to be repeated if they were completed within 14 days of Visit 1: hematology, chemistry, coagulation, complement activation factors, urinalysis, pregnancy test, and physical examination.

The following Visit 2 clinical, laboratory evaluations do not need to be repeated if they were completed within 14 days of the last study visit from the core GED-0301 study (or within 14 days of the combined Visit 1 and last study visit from the core GED-0301 study): hematology, chemistry, coagulation, complement activation factors, urinalysis,

pregnancy test, [REDACTED], physical examination, CDAI, [REDACTED]
[REDACTED]

The following evaluations will be performed at the frequency specified in [Table 5](#) for adult subjects and [Table 6](#) for adolescent subjects. The evaluations should be performed prior to dosing on the visit day, unless otherwise specified.

- Inclusion/exclusion criteria: Subjects must meet all inclusion criteria (Section 4.2) and must not have any of the conditions specified in the exclusion criteria (Section 4.3) to qualify for participation in the study, up through the day of enrollment at the Enrollment Visit 2.
- Prior and concomitant procedures evaluation (continuously assessed)
- Prior and concomitant medications evaluation (continuously assessed)
- AE evaluation (continuously assessed)
- Pregnancy test: A local urine pregnancy test will be performed on all FCBP at the Enrollment Visit, and the visits identified in [Table 5](#) and [Table 6](#). A local urine test will be performed by the site at the Enrollment Visit, prior to administration of IP, to ensure an immediate, negative test result. All local urine pregnancy test kits will be provided by the central laboratory. Urine and serum pregnancy tests should be performed if the FCBP has missed a menstrual period, or the contraception method has changed at any time during the study.
- Contraception education
- Vital signs and weight
- Height, only for the adolescent subjects and should be measured using a stadiometer.
- Physical examinations: The following physical examinations will be performed based on the Table of Events as specified in [Table 5](#) and [Table 6](#) and as described in Section 6.5.1:
 - Complete physical examination
 - Limited physical examination
(A limited physical examination is not done, if Visit 1 and Visit 2 are combined and/or completed on the same day as the last study visit in the core GED-0301 study. In this case, only a complete physical examination is done.)
 - Abdominal examination
(An abdominal examination for the abdominal mass assessment is completed for the CDAI, [REDACTED] and PCDAI calculations when physical examinations are not done.)
- 12-lead ECG
- Clinical laboratory evaluations (Section 6.5.3) according to the timeframes in [Table 5](#) and [Table 6](#)

[REDACTED]

- Dispense IP: The IP will be dispensed to the subject as specified in [Table 5](#), [Table 6](#) and Section [7.2](#). The subject should take the first dose in the office at the study site at the Enrollment Visit 2, and be witnessed by the site personnel. However, the IP can be dispensed to the subject at a combined Visit 1 and 2, if the GED-0301-CD-004 IP is available for the subject at the study center.
 - **The Principal Investigator, Sub-investigator or Study Coordinator should actually witness, if possible, the subject taking the first dose, and record date and time in the source document record.** The IP, four 40-mg tablets or matching placebo, should be taken by the subject once daily during the Long-term Active Treatment Period. Subjects will be instructed to take 4 tablets in the morning, 30 minutes before breakfast with a glass of water, and they will also be instructed to refer to the label for storage instructions.
- Return and count IP: A detailed record of the doses taken and doses missed between visits and at visits should be recorded in the Study Drug Record eCRF and the subject's source documents. Also, a record of the overall number of tablets dispensed and tablets returned at each visit must be maintained in the subject's source documents and recorded in the Drug Accountability eCRF.

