4.2. Inclusion Criteria

4.2.1. Inclusion Criteria for Adult Subjects

Adult subjects must satisfy the following criteria to be screened and enrolled in the study:

1. Subject is a male or female ≥ 18 years of age at the time of signing the informed consent form (ICF).
2. Subject must understand and voluntarily sign an ICF prior to any study-related assessments/procedures being conducted.
3. Subject is willing and able to adhere to the study visit schedule and other protocol requirements.
4. Subject must have completed through the Week 12 Visit in the core GED-0301 study **AND** either:
 - Completed participation through the last study treatment visit at Week 52 in Study GED-0301-CD-002 or at Week 12 in Study GED-0301-CD-003
 - OR**
 - Met the “early escape criteria” ([Appendix H](#)) and were discontinued beginning at the Week 12 Visit in Study GED-0301-CD-002.
5. Females of childbearing potential (FCBP)¹ must have a negative pregnancy test at screening and enrollment (Visits 1 and 2). FCBP must either practice true abstinence² from heterosexual contact or use one of the approved contraceptive options as described below while on IP and for at least 28 days after taking the last dose of IP:

¹ A female of childbearing potential is a sexually mature female who: 1) has not undergone a hysterectomy (the surgical removal of the uterus) or bilateral oophorectomy (the surgical removal of both ovaries); or 2) has not been postmenopausal for at least 24 consecutive months (that is, has had menses at any time during the preceding 24 consecutive months).

² True abstinence is acceptable when this is in line with the preferred and usual lifestyle of the subject. Periodic abstinence (eg, calendar, ovulation, symptothermal, post-ovulation methods) and withdrawal are not acceptable methods of contraception.

Option 1: Any one of the following highly effective methods: hormonal contraception (oral³, injection, implant, transdermal patch, vaginal ring); intrauterine device (IUD); tubal ligation; or partner's vasectomy

OR

Option 2: Male or female condom PLUS 1 additional barrier method: (a) diaphragm with spermicide; (b) cervical cap with spermicide; or (c) contraceptive sponge with spermicide

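### When Visit 2 is a separate visit, criterion 5 and Section 6.2 require a pre-dose pregnancy test there, but the 14-day waivers let a site omit it

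*Protocol*

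**What the plan says.** **Provisions that require a test at Visit 2**

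- Criterion 5 (Protocol 4.2.1 for adults, same wording in 4.2.2 for adolescents): females of childbearing potential "must have a negative pregnancy test at screening and enrollment (Visits 1 and 2". It mentions no waiver.
- Protocol 6.2, pregnancy-test bullet: "A local urine pregnancy test will be performed on all FCBP at the Enrollment Visit". The next sentence says the test is "performed by the site at the Enrollment Visit, prior to administration of IP, to ensure an immediate, negative test result".
- Protocol 6.2, eligibility bullet: the inclusion criteria must hold up to and including the day of Visit 2.

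**Provisions that waive it**

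- Protocol 6.2, first waiver: "The following Visit 2 clinical and laboratory evaluations do not need to be repeated if they were completed within 14 days of Visit 1". The list includes the pregnancy test.
- Protocol 6.2, second waiver: a longer list, again with the pregnancy test, of evaluations that "do not need to be repeated if they were completed within 14 days of the last study visit from the core GED-0301 study".
- Protocol 6.1.1, three-visit waiver: if the last core visit, Visit 1 and Visit 2 "are done separately but all are within a 14-day period, the following clinical, and laboratory evaluations do not need to be repeated", provided they were done at the last core visit. The pregnancy test is on this list too.
- Tables 5 and 6: the Visit 2 pregnancy-test cell carries superscript a. That footnote refers back to Sections 6.1.1 and 6.2.

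**The concern.** The same test at the same visit is both required and waived, and no sentence states which provision governs. A site that relies on a waiver gives the first dose on a test that cannot detect a conception after it was taken. It also enrolls the subject without a test that an eligibility criterion assigns to that visit.

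What is at stake is a patient-safety safeguard that the protocol itself states. Section 6.5.5 says there are no data on the drug in pregnant women and that animal data are limited. For former placebo subjects, the first dose here is their first exposure to GED-0301.

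**Working it through.** No sample size, power or error rate is involved. The check sets the provisions side by side, with simple day counts.

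**Step 1. When the conflict arises.** Section 6.1.1 lets Visits 1 and 2 be combined. One same-day test then serves both visits and nothing conflicts. The point is confined to a Visit 2 held on its own day.

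**Step 2. Whether the exception is written into the requirement.** Elsewhere the drafters put exceptions inside the bullet:

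- The Visit 1 pregnancy-test bullet (6.1.1) excuses the test if it was done at the last core visit.
- The limited physical examination bullet (6.2) says when that examination is not done.
- The Visit 2 pregnancy-test bullet has no such clause. It gives a purpose instead, an immediate negative result before dosing, which a result from an earlier day cannot serve.

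**Step 3. Whether the table footnote settles it.** It does not. The bullet names the Enrollment Visit first and then, separately, the visits marked in Tables 5 and 6. The Enrollment Visit test therefore does not depend on the table cell or its superscript.

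**Step 4. Age of the last test at first dose.**

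- Test done at Visit 2 as the bullet requires: 0 days.
- Intended reading of the waivers: last core visit, Visit 1 and Visit 2 all fall within 14 days, so a core-visit test is at most about 14 days old. In this case neither of the two visits named in criterion 5 has a test of its own.

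**Step 5. Anchor of the first Section 6.2 waiver.** The 14 days are counted from Visit 1. A test done at Visit 1 is 0 days from Visit 1, so the condition is always met, however long afterwards Visit 2 takes place. As worded, this waiver does not limit test age at Visit 2. The three-visit rule and footnote a suggest that 14 days before Visit 2 was meant.

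**Step 6. Who receives active drug at once.** The Week 0 column of Table 7, in row order, reads 160 mg, 160 mg, placebo, 40 mg, placebo. That is 3 of 5 regimens starting on active drug. Both former-placebo groups fall in the two 160 mg rows.

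**Step 7. Next scheduled test.** Week 24, with or without the waiver (Tables 5 and 6).

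**The case against.** The strongest defence is that the waivers are specific exceptions to a general rule. Saying that an evaluation need not be repeated presupposes a requirement and relaxes it. Section 6.2 ties its evaluations to the tables, whose Visit 2 pregnancy-test and eligibility cells both carry superscript a. The change was deliberate: the amendment's summary names the pregnancy test among the items not repeated and gives reduced burden as the reason. This reading is plausible and stands as an account of intent. It does not amend criterion 5, and it does not reconcile the waiver with the purpose stated in the bullet.

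The second defence is that the risk is small, and this largely stands:

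- Pregnancy is an exclusion (4.3), and contraception must be effective by enrollment (6.5.5).
- A missed period or a change of contraception triggers urine and serum tests (6.2).
- Systemic bioavailability is described as negligible at up to 160 mg/day for 7 days (1.2.2.1).
- Two of the five regimens begin with four weeks of placebo (Table 7).
- Scheduled tests fall at Weeks 0, 24, 52, 80, 104, 128, 156, 184 and 208, so the protocol already accepts gaps of 24 to 28 weeks during treatment.

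These facts limit the consequence. They do not remove the contradiction about the one test that the protocol ties to the moment before first dosing.

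A reader might go further and infer that any site using a waiver has committed an eligibility violation. The documents do not support so firm a statement. On the exception reading, a carried-over negative result stands in for the Visit 2 result, and the text does not say which reading governs.

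**Conclusion.** The inconsistency is real and lies in current protocol text. With a separate Visit 2, criterion 5 and the Section 6.2 bullet require a pre-dose test that three waivers excuse. The effect is that the last test may be up to about 14 days old at first dose instead of 0. This assumes the three-visit rule and footnote a show the intended window.

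A reader might infer a ceiling of 28 days from the literal wording of the first Section 6.2 waiver, because Visit 1 may fall on Day -28 and Section 6.1 says screening evaluations "must be completed within 28 days prior to the date of the first dose of IP (study enrollment". That figure should not be quoted. The Section 6.1 sentence goes on to allow for exceptions noted later. On the same literal wording, a core-visit test 14 days before a Day -28 Visit 1 would also qualify, at 28 + 14 = 42 days. The wording gives no dependable upper bound. What can be said is that the first waiver fails to set the 14-day limit it appears to intend.

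The risk is modest and no safety or efficacy analysis depends on it. The documents do not say how many women would have a separate Visit 2. For adolescents the conflict is textual only, because SAP Section 4.1 states that Study GED-0301-CD-003 was not initiated. The early termination described in SAP Section 2 limits the practical effect for adults as well.

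**What to change.** - Remove the pregnancy test from both Visit 2 waiver lists in Section 6.2 and, as far as Visit 2 is concerned, from the three-visit list in Section 6.1.1.
- In Tables 5 and 6, limit superscript a on the Visit 2 pregnancy-test cell to visits combined on the same day.
- For the evaluations that stay on the first Section 6.2 list, count the window as within 14 days before Visit 2.

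Making criterion 5 and the bullet subject to the waivers would also remove the contradiction, but it would give up the immediate pre-dose result.

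The cost is amendment wording, with written IRB/IEC approval before implementation (Section 13.5), and one extra urine test for some women, using kits the central laboratory already provides. If no amendment is made because the study has stopped, the sponsor should at least record which rule governed.

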Complete Physical Examination	-	-	-	-	-	-	-	-	-	-	-	-	-
Limited Physical Examination	-	-	-	-	-	-	-	-	-	-	-	-	X
12-lead ECG	-	-	-	-	-	-	-	-	-	-	-	-	X
Clinical Lab (Hematology)	-	-	-	-	-	-	X	-	-	-	-	-	X
Clinical Lab (Chemistry)	-	-	-	-	-	-	X	-	-	-	-	-	X
Clinical Lab (Coagulation)	-	-	-	-	-	-	X	-	-	-	-	-	X
Clinical Lab (Complement Activation Factor)	-	-	-	-	-	-	X	-	-	-	-	-	X
Clinical Lab (Urinalysis)	-	-	-	-	-	-	X	-	-	-	-	-	X

Table 5: Table of Events for Adult Subjects (Years 1 to 4) (Continued)

	Long-term Active Treatment Period (Year 2)												
Visit Number	16	17	18	19	20	21	22	23	24	25	26	27	28
Week	56	60	64	68	72	76	80	84	88	92	96	100	104
Visit Window	(± 3 days)	(± 3 days)	(± 3 days)	(± 3 days)	(± 3 days)	(± 3 days)	(± 3 days)	(± 3 days)	(± 3 days)	(± 3 days)	(± 3 days)	(± 3 days)	(± 3 days)
Dosing													
Dispense IP	X	X	X	X	X	X	X	X	X	X	X	X	X
Return and Count IP	X	X	X	X	X	X	X	X	X	X	X	X	X

Table 5: Table of Events for Adult Subjects (Years 1 to 4) (Continued)

	Long-term Active Treatment Period (Year 3)												
Visit Number	29	30	31	32	33	34	35	36	37	38	39	40	41
Week	108	112	116	120	124	128	132	136	140	144	148	152	156
Visit Window	(± 3 days)	(± 3 days)	(± 3 days)	(± 3 days)	(± 3 days)	(± 3 days)	(± 3 days)	(± 3 days)	(± 3 days)	(± 3 days)	(± 3 days)	(± 3 days)	(± 3 days)
Safety Assessments^b													
Prior / Concomitant Medications and Procedures	X	X	X	X	X	X	X	X	X	X	X	X	X
Adverse Events	X	X	X	X	X	X	X	X	X	X	X	X	X
Pregnancy Test	-	-	-	-	-	X	-	-	-	-	-	-	X
Contraception Education	-	-	-	-	-	X	-	-	-	-	-	-	X
Vital Signs / Weight	-	X	-	-	-	X	-	-	-	X	-	-	X
Complete Physical Examination	-	-	-	-	-	-	-	-	-	-	-	-	-
Limited Physical Examination	-	-	-	-	-	-	-	-	-	-	-	-	X
12-lead ECG	-	-	-	-	-	-	-	-	-	-	-	-	X
Clinical Lab (Hematology)	-	-	-	-	-	X	-	-	-	-	-	-	X
Clinical Lab (Chemistry)	-	-	-	-	-	X	-	-	-	-	-	-	X
Clinical Lab (Coagulation)	-	-	-	-	-	-	-	-	-	-	-	-	X
Clinical Lab (Complement Activation Factor)	-	-	-	-	-	-	-	-	-	-	-	-	X
Clinical Lab (Urinalysis)	-	-	-	-	-	X	-	-	-	-	-	-	X

Table 5: Table of Events for Adult Subjects (Years 1 to 4) (Continued)

	Long-term Active Treatment Period (Year 3)												
Visit Number	29	30	31	32	33	34	35	36	37	38	39	40	41
Week	108	112	116	120	124	128	132	136	140	144	148	152	156
Visit Window	(± 3 days)	(± 3 days)	(± 3 days)	(± 3 days)	(± 3 days)	(± 3 days)	(± 3 days)	(± 3 days)	(± 3 days)	(± 3 days)	(± 3 days)	(± 3 days)	(± 3 days)
Dosing													
Dispense IP	X	X	X	X	X	X	X	X	X	X	X	X	X

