7.2. Treatment Administration and Schedule

Beginning at Week 0 through Week 12, subjects will receive blinded-active GED-0301 (160 mg QD or 40 mg QD) treatment as one of the following numbered treatment groups:

- 1) continuous 160 mg QD for 12 weeks;
- 2) 160 mg QD for 4 weeks, PBO QD for 4 weeks, 160 mg QD for 4 weeks;
- 3) PBO QD for 4 weeks, 160 mg QD for 4 weeks, PBO QD for 4 weeks;
- 4) continuous 40 mg QD for 12 weeks;
- 5) PBO QD for 4 weeks, 40 mg QD for 4 weeks, PBO QD for 4 weeks.

Beginning at Week 12 through Week 208, subjects from the above-numbered treatment groups will continue to receive blinded-active GED-0301 treatment for 196 weeks as the following:

- 1) alternating PBO QD for 4 weeks with 160 mg QD for 4 weeks, through Week 208;
- 2) alternating PBO QD for 4 weeks with 160 mg QD for 4 weeks, through Week 208;
- 3) alternating 160 mg QD for 4 weeks with PBO QD for 4 weeks, through Week 208;
- 4) continuous 40 mg QD, through Week 208;
- 5) alternating 40 mg QD for 4 weeks with PBO QD for 4 weeks, through Week 208.

Subjects will receive 1 blister card when IP is administered. Four tablets are taken once daily during the 208-week Long-term Active Treatment Period. Subjects will be instructed to take 4 tablets in the morning, 30 minutes before breakfast with a glass of water, and they will also be instructed to refer to the label for storage instructions.

Please note: All 160 mg QD treatments are taken as four 40 mg tablets once daily in the study.

Treatment and administration schedules are described in Table 7, Table 8, Table 9, and Table 10.

The treatment described in each box is the treatment dispensed at a particular week visit. For example, if the subject was previously on PBO (with no clinical improvement) in the core GED-0301 study, the subject would receive the IP in this study as:

- blinded GED-0301 160 mg QD for a 4-week supply at the Week 0 Visit;
- blinded GED-0301 160 mg QD for a 4-week supply at the Week 4 Visit;
- blinded GED-0301 160 mg QD for a 4-week supply at the Week 8 Visit;
- blinded PBO QD for a 4-week supply at the Week 12 Visit;
- alternating blinded GED-0301 160 mg QD for a 4-week supply followed by blinded PBO QD for a 4-week supply at Week 16 through Week 208; and
- no IP at the Week 208 Visit.

Table 7: Investigational Product Dispensing Schedule for the Treatment Period at Year 1

Treatment Group from Core GED-0301 Study	Long-term Active Treatment Period (All Treatment is Blinded) (Year 1)													

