	Week 0	Week 4	Week 8	Week 12	Week 16	Week 20	Week 24	Week 28	Week 32	Week 36	Week 40	Week 44	Week 48	Week 52
PBO (with no improvement)	160 mg QD	160 mg QD	160 mg QD	PBO QD	160 mg QD	PBO QD	160 mg QD	PBO QD	160 mg QD	PBO QD	160 mg QD	PBO QD	160 mg QD	PBO QD
GED-0301 40 mg or 160 mg on/off, or 40 mg daily, or 160 mg QD for 12 weeks (with no improvement), or PBO (with improvement)	160 mg QD	PBO QD	160 mg QD	PBO QD	160 mg QD	PBO QD	160 mg QD	PBO QD	160 mg QD	PBO QD	160 mg QD	PBO QD	160 mg QD	PBO QD
GED-0301 160 mg on/off or 160 mg QD for 12 weeks (with improvement)	PBO QD	160 mg QD	PBO QD	160 mg QD	PBO QD	160 mg QD	PBO QD	160 mg QD	PBO QD	160 mg QD	PBO QD	160 mg QD	PBO QD	160 mg QD
GED-0301 40 mg daily (with improvement)	40 mg QD	40 mg QD	40 mg QD	40 mg QD	40 mg QD	40 mg QD	40 mg QD	40 mg QD	40 mg QD	40 mg QD	40 mg QD	40 mg QD	40 mg QD	40 mg QD
GED-0301 40 mg on/off (with improvement)	PBO QD	40 mg QD	PBO QD	40 mg QD	PBO QD	40 mg QD	PBO QD	40 mg QD	PBO QD	40 mg QD	PBO QD	40 mg QD	PBO QD	40 mg QD

PBO = placebo; QD = once daily.

Table 8: Investigational Product Dispensing Schedule for the Treatment Period at Year 2

Treatment Group from Core GED-0301 Study	Long-term Active Treatment Period (All Treatment is Blinded) (Year 2)												
	Week 56	Week 60	Week 64	Week 68	Week 72	Week 76	Week 80	Week 84	Week 88	Week 92	Week 96	Week 100	Week 104
PBO (with no improvement)	160 mg QD	PBO QD	160 mg QD	PBO QD	160 mg QD	PBO QD	160 mg QD	PBO QD	160 mg QD	PBO QD	160 mg QD	PBO QD	160 mg QD
GED-0301 40 mg or 160 mg on/off, or 40 mg daily, or 160 mg QD for 12 weeks (with no improvement), or PBO (with improvement)	160 mg QD	PBO QD	160 mg QD	PBO QD	160 mg QD	PBO QD	160 mg QD	PBO QD	160 mg QD	PBO QD	160 mg QD	PBO QD	160 mg QD
GED-0301 160 mg on/off or 160 mg QD for 12 weeks (with improvement)	PBO QD	160 mg QD	PBO QD	160 mg QD	PBO QD	160 mg QD	PBO QD	160 mg QD	PBO QD	160 mg QD	PBO QD	160 mg QD	PBO QD
GED-0301 40 mg daily (with improvement)	40 mg QD	40 mg QD	40 mg QD	40 mg QD	40 mg QD	40 mg QD	40 mg QD	40 mg QD	40 mg QD	40 mg QD	40 mg QD	40 mg QD	40 mg QD
GED-0301 40 mg on/off (with improvement)	PBO QD	40 mg QD	PBO QD	40 mg QD	PBO QD	40 mg QD	PBO QD	40 mg QD	PBO QD	40 mg QD	PBO QD	40 mg QD	PBO QD

PBO = placebo; QD = once daily.

Table 9: Investigational Product Dispensing Schedule for the Treatment Period at Year 3

Treatment Group from Core GED-0301 Study	Long-term Active Treatment Period (All Treatment is Blinded) (Year 3)												

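### Pre-dose lab draws alias with the 8-week on/off cycle, and the pooled GED 160 ALT lab tables mix on-drug and off-drug values without marking which is which.

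*Protocol*

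**What the plan says.** Protocol 6.2 sets the timing of assessments on a visit day: "The evaluations should be performed prior to dosing on the visit day, unless otherwise specified". It also fixes the visits to enrolment: "All subsequent visits after the Enrollment Visit (which is the Visit 2/Week 0 Visit) are scheduled based on the date of the Visit 2/Week 0", with a window of 3 days either way. Protocol 7.2 explains how to read the dispensing tables: "The treatment described in each box is the treatment dispensed at a particular week visit".

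Two regimens start on 160 mg. Regimen 1 opens with "1) continuous 160 mg QD for 12 weeks". Regimen 2 opens with "2) 160 mg QD for 4 weeks, PBO QD for 4 weeks, 160 mg QD for 4 weeks" and goes on with "2) alternating PBO QD for 4 weeks with 160 mg QD for 4 weeks, through Week 208"; regimen 1 follows the same alternation from Week 12. Regimens 3 (160 mg) and 5 (40 mg) start on placebo and run in the opposite phase. Regimen 4 is continuous 40 mg.

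Protocol Table 5 schedules chemistry after Week 0 at Weeks 12, 24, 40, 52, 80, 104, 128, 156, 184 and 208. Coagulation and complement use the same weeks without 128 and 184. The Week 40 entry carries a footnote c whose text is not legible.

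SAP 5.1 lists the five regimens separately in listings, but in tables combines every variant of the alternating 160 mg regimen as GED 160 ALT. SAP 12.3 summarises labs by time point, gives shift tables for hematology and chemistry that include the worst value, and counts marked abnormalities over Weeks 0-208. No legible text in either document relates a lab value to the on or off phase.

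**The concern.** Long-term safety is the primary objective, and the labs are the scheduled means of finding changes that cause no symptoms. If the lab grid and the dosing cycle move in step, whether a sample is taken on or off drug is set by sequence and visit number. A change that appears on GED-0301 and recovers within 4 weeks of placebo would then be seen in one sequence and not in the other at the same visit. A pooled visit mean would average the two, and movement between visits could come from phase alone.

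At stake is how the GED 160 ALT lab tables are read: a reader cannot tell how much of any figure was observed on drug.

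**Working it through.** **Inputs.** Lab weeks: Protocol Table 5. Blocks: Protocol Tables 7 to 10. Timing rule: Protocol 6.2. Pooling and summaries: SAP 5.1 and 12.3. The plan gives no figure of its own to reproduce.

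**Rule.** The draw is pre-dose, so a draw at Week w belongs to the block dispensed at Week w − 4. Visits are anchored to Week 0, so drift does not accumulate. Consecutive visits are at least 28 − 3 − 3 = 22 days apart, so the window does not move a draw into another block.

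**Chemistry.**

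| Draw (Week) | Block dispensed at Week | Regimens 1, 2 (160 mg first) | Regimens 3, 5 (placebo first) |
|---|---|---|---|
| 12 | 8 | active | placebo |
| 24 | 20 | placebo | active |
| 40 | 36 | placebo | active |
| 52 | 48 | active | placebo |
| 80 | 76 | placebo | active |
| 104 | 100 | placebo | active |
| 128 | 124 | placebo | active |
| 156 | 152 | active | placebo |
| 184 | 180 | placebo | active |
| 208 | 204 | placebo | active |

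The aliasing is exact. Every 160-mg-first draw after placebo falls at a multiple of 8 weeks, and every draw after active falls 4 weeks off such a multiple.

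**Counts of draws after an active block.**
- Chemistry, regimens 1 and 2: 3 of 10. Without the Week 40 draw: 3 of 9.
- Chemistry, regimens 3 and 5: 7 of 10, or 6 of 9 without Week 40. Regimen 4: 10 of 10.
- Coagulation and complement: 3 of 8 for regimens 1 and 2, 5 of 8 for regimens 3 and 5.
- Chemistry by period, regimens 1 and 2: Year 1 (Weeks 12, 24, 40, 52) 2 of 4; Weeks 80 to 208 1 of 6. Strictly between Weeks 52 and 156 there is none.

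**Effect of pooling.** Let p be the share of GED 160 ALT subjects with a value at a visit who started on 160 mg. From the table, the on-drug share of the pooled group is p at Weeks 12, 52 and 156, and 1 − p at the other seven visits. A mean shift δ that vanishes within 4 weeks off drug therefore appears as pδ or (1 − p)δ. The documents do not give p, so it may lie anywhere from 0 to 1. The on-drug share differs between the two kinds of visit by |2p − 1|, which is zero only at p = 1/2; even then each visit mean shows half of δ.

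**Who is in each phase.** In Appendix G, six CD-002 rows lead to the alternating 160 mg regimen. Five start on 160 mg: former placebo subjects with and without improvement, and non-improvers from each of the three GED-0301 regimens. One starts on placebo: improvers on alternating 160 mg. Phase at a given visit is thus tied to core-study history.

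**The case against.** Much of the case on the other side stands.

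A reader might infer that the highest regimen is hardly sampled on drug. It is not so: regimen 3 takes the same alternating 160 mg in the opposite phase and supplies on-drug values at all seven visits where regimens 1 and 2 do not. Five of six Appendix G rows are rows, not subjects; group sizes are not given.

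A reader might also infer that the imbalance runs through the whole study. Year 1 is balanced, and SAP 2 records early termination after an October 2017 recommendation of the Data Monitoring Committee. How many subjects reached Week 80 or later is not stated.

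Nor do the documents show that a safety effect was missed. The dilution needs an effect that recovers within 4 weeks. No passage reports one, and Protocol 1.2.2.1 describes systemic bioavailability as negligible (from 7 days of dosing). Persistent or cumulative changes would still show at off-drug draws. Adverse events are assessed continuously, unscheduled labs are allowed, and early termination visits carry full panels that can fall in either phase.

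Finally, the SAP listings show all lab data by the five regimens, and text between SAP 12 and 12.2 is blacked out, so handling of phase there cannot be excluded.

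What survives is narrower. Event-driven collection does not replace scheduled detection of silent changes, a listing is not a summary, and the legible tables leave the two phases mixed.

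**Conclusion.** The point holds as a limitation of the lab summaries with a cheap remedy. For 160-mg-first subjects, 3 of 10 scheduled post-baseline chemistry draws (3 of 9 if Week 40 does not apply) and 3 of 8 coagulation and complement draws follow an active block, with the skew confined to Weeks 80 to 208. The planned GED 160 ALT tables combine this with the opposite phase, so they mix on-drug and off-drug values, in a proportion that flips between visits unless the two sequences happen to be equal in number.

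This rests on the pre-dose rule applying to labs (no legible exception is given), on subjects following the dispensing tables, and on counting only scheduled draws after Week 0, without early termination and follow-up. The size of any dilution cannot be stated, because neither the sequence sizes nor the number of late draws is given.

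A reader might conclude that the Week 80 and Week 128 draws have to be moved. The documents do not support that as a required change. Moving them to Weeks 76 and 124 would give 160-mg-first subjects 5 of 10 on-drug draws, but placebo-first subjects would fall from 7 to 5 and acquire an on-drug gap of 184 − 104 = 80 weeks. Weeks 184 and 208 would remain off drug for 160-mg-first subjects, and the labs would be separated from the vital signs and pregnancy tests at the present visits. It is a trade-off, and the study has stopped.

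**What to change.** In SAP 12.3, derive for each lab record, including early termination and unscheduled draws, the IP block in use or just completed (GED or PBO), from dispensing and dosing dates. For the alternating regimens, present change from baseline and marked abnormalities by that flag, beside the planned pooled tables.

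The cost is one derived variable and a few extra tables; no new data are needed. One caution belongs in the text: at any single visit the on/off contrast within GED 160 ALT is confounded with core-study improvement status, so the flagged tables should be read mainly within subject across visits.

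For any future use of this design, it is enough to note that lab visits should be spread over both phases of the cycle for both sequences.
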